7 SELECTION OF PATIENTS

7.1 INCLUSION CRITERIA

I 01. Adult male or female patients.

I 02. Documented diagnosis of IPF according to the following criteria:

- Exclusion of other known causes of interstitial lung disease (e.g. domestic and occupational environmental exposures, connective tissue disease, and drug toxicity)*

AND

- Combination of patterns of usual interstitial pneumonia (UIP) on HRCT images of chest, and on surgical lung biopsy (when obtained)*

OR

Presence of Possible UIP pattern* on HRCT images of chest AND additional evidence of traction bronchiectasis as assessed by an experienced chest radiologist (Central Review**)

* As defined in the current 2011 ATS/ERS/JRS/ALAT guidelines

** The patterns of UIP on HRCT images of chest and histopathology in surgical lung biopsy (if done) will be reviewed by central reviewers (a radiologist and a pathologist experienced in interstitial lung diseases) to confirm diagnosis of IPF for consistency.

I 03. Signed written informed consent.

7.2 EXCLUSION CRITERIA

E 01. Age \leq 40 years.

E 02. IPF disease diagnosis $>$ 5 years.

E 03. Forced vital capacity (FVC) $<$ 40% of predicted value.

E 04. Carbon monoxide diffusing lung capacity (DLCO) corrected for hemoglobin $<$ 30% of predicted value.

E 05. Severe chronic obstructive bronchitis as characterized by FEV1/FVC $<$ 0.70.

- E 06. Need for 24 hrs of oxygen therapy or oxygen saturation <88% after 10 minutes breathing ambient air at rest.
- E 07. Known diagnosis of significant respiratory disorders (e.g. asthma, tuberculosis, sarcoidosis, aspergillosis, or cystic fibrosis) other than IPF.
- E 08. Pulmonary artery hypertension requiring a specific treatment.
- E 09. Currently listed and/or anticipated to be listed for lung transplantation within the next 6 months (on an active list).
- E 10. History of vasculitis or connective tissue disorders or ANCA positive.
- E 11. Known HIV or chronic viral hepatitis.
- E 12. Exclusion related to tuberculosis (TB):
- Active tuberculosis (according to WHO guidelines (25) or a history of incompletely treated tuberculosis
 - Incompletely treated latent tuberculosis (according to WHO guidelines)
 - Positive or confirmed indeterminate (2 consecutive tests) QuantiFERON-TB Gold® test at screening (regardless of prior treatment status)
- E 13. Evidence of any clinically significant, severe or unstable, acute or chronically progressive medical (other than IPF) or surgical disorder, or any condition that may affect patient safety in the judgment of the investigator.
- E 14. Acute myocardial infarction within 6 months prior to screening.
- E 15. Clinically significant abnormal electrocardiogram (ECG) at screening that may affect the conduct of the study in the judgement of the investigator.
- E 16. Clinically significant laboratory tests at screening:
- Alanine transaminase (ALT) or aspartate transaminase (AST) >2 times upper limit of normal range (ULN)
 - Hemoglobin <11 g/100 mL for male and <10 g/100 mL for female
 - Neutrophils <1500/mm³ (except <1000/mm³ for those of African descent)
 - Platelets <100 000/mm³
 - Creatinine ≥150 µmol/L
- E 17. Current history of substance and/or alcohol abuse.

E 18. Females who are lactating or who are pregnant.

E 19. Women who are of childbearing potential not protected by highly-effective contraceptive method(s) of birth control (as defined in the informed consent form and /or in a local protocol addendum/amendment), and/or who are unwilling or unable to be tested for pregnancy.

For Denmark only, per local requirement: Acceptable methods of contraception include:

- *Intra-uterine devices (IUD);*
- *Hormonal contraceptives (contraceptive pills, implants, transdermal patches, hormonal vaginal devices or injections with prolonged release).*

For UK only, per local requirement: Acceptable forms of effective contraception include:

- *Established use of oral, intravaginal, or transdermal combined (estrogen and progestogen containing) hormonal contraception associated with inhibition of ovulation*
- *Established use of oral, injectable, or implantable progestogen-only hormonal contraception associated with inhibition of ovulation*
- *Placement of an intrauterine device (IUD) or intrauterine hormone-releasing system (IUS)*
- *Bilateral tubal occlusion*
- *Male sterilisation (provided that the partner is the sole sexual partner of the woman of childbearing potential study participant and that the sterilized partner has received medical assessment of the surgical success.)*
- *True abstinence: When this is in line with the preferred and usual lifestyle of the subject. (Periodic abstinence (eg, calendar, ovulation, symptothermal, post-ovulation methods) and withdrawal are not acceptable methods of contraception).*

Note: Women of childbearing potential must have a confirmed negative pregnancy test at screening and baseline visits. Postmenopausal women must be amenorrhic for at least 12 months. Women of childbearing potential must use an effective contraceptive method throughout the entire duration of the study treatment and for 12 weeks after the last investigational medicinal product administration.

[For Czech Republic only, per local requirement:

E.19 Women who are of childbearing potential not protected by highly-effective contraceptive method(s) of birth control and/or who are unwilling or unable to be tested for pregnancy.

Male participants with a female partner of childbearing potential not protected by highly effective contraceptive method(s) of birth control.

- *Acceptable methods of contraception include:*
 - *Method with reliability index <1 (such as IUD, sterilization of one of the partners provided that this partner is the only one for whole duration of the clinical trial, further hormonal implants, injections, patches, oral hormonal contraception) plus one supplementary barrier method of contraception always with spermicide. Men should always use condom.*
 - *These methods must be used during whole study treatment duration and 3 months after the end of the investigational product administration*

Note: Women of childbearing potential must have a confirmed negative pregnancy test at screening and baseline visits. Postmenopausal women must be amenorrheic for at least 12 months.]

- E 20. Use of any cytotoxic/immunosuppressive agent including but not limited to azathioprine, cyclophosphamide, methotrexate, and cyclosporine within 4 weeks prior to screening.
- E 21. Use of any cytokine modulators (etanercept, adalimumab, efalizumab, infliximab, golimumab, certolizumab, rituximab) within 12 weeks or 5 half-lives of screening (24 weeks for rituximab and 24 months for alefacept).
- E 22. Use of any investigational drug within 1 month of screening, or 5 half-lives, if known (whichever is longer), or within 12 weeks for stem cell therapy.

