8.8.1 Prohibited medications

- Use of any cytotoxic/immunosuppressive (other than prednisone less than or equal to 10 mg/day or equivalent) including but not limited to azathioprine, cyclophosphamide, methotrexate, and cyclosporine within 4 weeks prior to screening and during the course of the study.
- Use of any cytokine modulators
 - Use of any biologic agent (such as etanercept, adalimumab, efalizumab, infliximab, golimumab, certolizumab) within 12 weeks or 5 half-lives of screening, and in the case of rituximab, use within 24 weeks of screening or no recovery of CD 19-positive B lymphocytes if the last dose of rituximab has been more than 24 weeks prior to screening. The use of these biologic agents is not authorized during the course of the study.
 - Alefacept within 24 months of screening and during the course of the study.
- Use of any investigational drug within 1 month of screening, or 5 pharmacodynamic/pharmacokinetic half-lives, if known (whichever is longer), and during the course of the study. Use of stem cell therapy within 12 weeks of screening, and during the course of the study.

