8.8.2 Authorized concomitant medications

- Oral corticosteroids are permitted if ≤ 10 mg/day oral prednisone or equivalent and at stable dose for at least 4 weeks prior to the randomization (baseline) visit. No change is permitted unless the patient develops an AE. Dose and any change will be recorded on the patient e-CRF.
- Pirfenidone or nintedanib administered at the recommended dosage for at least 12 weeks prior to the randomization (baseline). No change is permitted unless the patient develops an AE. Dose and any change will be recorded on the patient e-CRF. Pirfenidone or nintedanib cannot be started during the course of the study.

[For Czech Republic only, per local requirement:

- *N-acetylcysteine administered at the dosage recommended by local guidelines]*

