10 STUDY PROCEDURES

10.1 VISIT SCHEDULE

It is preferred that all study visits take place in the morning when fasting blood samples are required.

The study visits occur on the planned dates (relative to the first injection), as scheduled. The visit schedule should be adhered to within the ± 2 day visit window.

If a patient is prematurely discontinued from treatment, all assessments planned at the End of Treatment visit should be performed.

Prior to all screening assessments, after discussion of participation in the study, the written consent form (including voluntary participation in pharmacogenetic testing and for future use of samples) must be signed and dated.

[figure not shown]
Although the screening assessments for this study are grouped under the heading of a single visit in this protocol, it is possible for them to be performed over more than 1 site visit if necessary, as long as the screening visit window prior to Day 1 is respected. Patients that fail screening for exclusion criteria, e.g. concomitant medications, required drug-specific discontinuation periods or laboratory tests, may be rescreened for study eligibility 1 additional time (refer to [Section 8.4](#) for further instructions related to rescreening).

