10.1.1 Visit 1: Screening (D-28 to D-1)

Following a discussion of participation in the clinical trial, informed consent must be obtained and documented. These steps precede any study procedures.

The following procedures will then be performed:

- Call IVRS to assign a patient number
- Record patient demographic information
- Assess eligibility by review of Inclusion /Exclusion Criteria. This includes the review of prior and concomitant medications
- Commence AE reporting
- Patients who do not meet these inclusion/exclusion criteria should not continue the screening process and a screen failure call should be done in the IVRS

- Interview to collect:
 - IPF history
 - Months since IPF diagnosis;
 - IPF diagnostic algorithm (eg. diagnosis by HRCT and/or surgical biopsy);
 - History of acute exacerbation of IPF (most recent event within the past 12 months prior to randomization, in accordance with published definitions)
 - Family history of IPF
 - Other medical/surgical history and smoking habits
 - Recording of all prior significant medical conditions, and/or hospitalization history, eg. pneumonia, asthma, Chronic obstructive pulmonary disease (COPD), diabetes, hypertension, pulmonary arterial hypertension, congestive heart failure, esophageal reflux, depression, sleep apnea, myocardial infarction or arrhythmias, need for major surgery or surgical complications.
 - Recording current smoking status (current or recent smoking during the year prior to enrollment) and past smoking history (prior habitual smoking more than 1 year prior to enrollment).
- Record vital signs including blood pressure, heart rate, weight (kg) and height (cm) (collected for Body Mass Index calculation)
- Perform a complete physical examination: nasal cavities, eyes, ears, respiratory, cardiovascular, gastrointestinal, neurological, lymphatic, musculoskeletal systems, and skin. Gynecological and urogenital examinations will not be done unless for cause.
 - 
Nail beds (periungual areas) should be examined for "splinter lesions" and digital tuft for tuft purpura or ischemia.
- Obtain (fasting) blood samples for screening laboratory determinations: hematology, biochemistry, serology tests (hepatitis B surface antigen, hepatitis B surface antibody, hepatitis B core antibody, hepatitis C antibodies), and serum β -HCG plasma test if female of childbearing potential
- Perform blood sample for ANCA
- Perform blood sample for complement (C3, C4 and CH50)

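### Exclusion criterion E 21 omits the B-cell recovery condition that Protocol Section 8.8.1 sets for earlier rituximab

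*Protocol*

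**What the plan says.** **Rituximab.** E 21 in Protocol 7.2 excludes recent users of cytokine modulators. The general window is 12 weeks or 5 half-lives before screening, with two exceptions: "24 weeks for rituximab and 24 months for alefacept". Nothing in E 21 concerns B-cell status. Section 8.8.1 covers the same drugs and also counts back from screening. For rituximab it prohibits use within 24 weeks, and in addition it prohibits the case of "no recovery of CD 19-positive B lymphocytes if the last dose of rituximab has been more than 24 weeks prior to screening".

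**Immunosuppressants.** E 20 excludes "Use of any cytotoxic/immunosuppressive agent including but not limited to azathioprine, cyclophosphamide, methotrexate, and cyclosporine within 4 weeks prior to screening". Section 8.8.1 repeats the drug list and the 4-week window, with a parenthesis: "Use of any cytotoxic/immunosuppressive (other than prednisone less than or equal to 10 mg/day or equivalent". Section 8.8.2 permits oral corticosteroids up to "10 mg/day oral prednisone or equivalent", provided the dose has been stable for at least 4 weeks before the randomization visit.

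**How eligibility is decided.** Section 8.4 assigns treatment to patients who comply with the inclusion and exclusion criteria, and Section 10.1.2 repeats that condition before the randomization call. At screening, Section 10.1.1 says of the eligibility assessment: "This includes the review of prior and concomitant medications".

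**The concern.** Section 8.8.1 is more than an on-study ban. Its windows start before screening, so in effect it sets entry rules for drugs that 7.2 also regulates. The two sections should match. For rituximab they do not, and the shorter rule sits in the list that controls entry.

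Section 10.1.1 bases screen failure on that list: "Patients who do not meet these inclusion/exclusion criteria should not continue the screening process". A site that checks rituximab against E 21 and finds a last dose more than 24 weeks back has no reason within 7.2 to ask about B-cell recovery. The patient could then be randomized to an antibody against IL-4 and IL-13 while in a state that 8.8.1 prohibits.

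What is at stake is a safety-type restriction and the consistent classification of such a patient. SAP 2.2.1 counts randomization of an ineligible patient as an irregularity, and SAP 2.4.2 reports prohibited medications in the deviations table. The patient described here would be eligible under 7.2 and in breach of 8.8.1.

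**Working it through.** The plan gives no figure to reproduce and no arithmetic applies. The check sets the two rules side by side.

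**Rituximab: E 21 against 8.8.1 (illustrative patients)**

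| Last dose before screening | CD19-positive B cells | E 21 | 8.8.1 |
|---|---|---|---|
| 20 weeks | any status | bars | bars |
| 25 weeks | recovered | does not bar | does not bar |
| 25 weeks | not recovered | does not bar | bars |

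The rules part only in the last row. That row is the whole class of patients beyond 24 weeks without recovery, so the gap does not depend on the choice of 25 weeks. A patient at 30 weeks without recovery gives the same result. The other limits agree between the sections: 12 weeks or 5 half-lives for the other biologics, and 24 months for alefacept.

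**Which rule governs entry.** Sections 8.4 and 10.1.2 both name the inclusion and exclusion criteria. Neither refers to 8.8.1, and E 21 contains no cross-reference to it.

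**Prednisone: E 20 against 8.8.1 and 8.8.2**

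1. E 20 read alone names azathioprine, cyclophosphamide, methotrexate and cyclosporine as examples. It does not mention corticosteroids.
2. The text that places prednisone in the class is the parenthesis in 8.8.1, and that same parenthesis exempts 10 mg/day or less.
3. Reading prednisone into E 20 on the strength of 8.8.1 therefore brings the exemption with it.
4. The stable-dose rule in 8.8.2 is tied to the randomization visit, so it has a purpose only if such patients can enrol.
5. SAP 2.4.2 plans to summarize how many patients take systemic corticosteroids at randomization, with dose in prednisone equivalents. SAP Appendix F codes corticosteroids separately from the E 20 class.

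The rituximab difference is thus a condition present in one section and absent from the other. The prednisone difference disappears once the sections are read together.

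**The case against.** The strongest reply is that E 21 and 8.8.1 are not contradictory. E 21 never says that everyone beyond 24 weeks is eligible, and a site can obey both sections by applying the stricter one. The protocol also steers sites that way. Section 10.1.1 makes medication review part of the eligibility assessment. Section 10.1 describes rescreening for "Patients that fail screening for exclusion criteria, e.g. concomitant medications, required drug-specific discontinuation periods or laboratory tests". Section 13.1 requires compliance with all protocol procedures, and E 13 lets the investigator exclude on safety grounds.

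Most of this stands. E 21 has an omission and is not logically incompatible with 8.8.1. A site that consults 8.8.1 during medication review reaches the intended answer, which is why the point is minor. The reply does not remove the gap, however. The medication review in 10.1.1 does not point to 8.8.1, and E 13 leaves the decision to judgement without stating the CD19 rule.

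Two stronger readings are tempting. A reader might infer that E 20 and 8.8.1 give opposite rules for low-dose prednisone, so that the protocol turns away patients it means to allow. The documents do not support that, for the reasons set out in the prednisone steps above. A reader might also infer that the protocol lacks any means of checking CD19 at screening. That cannot be established, because the flow chart and the SAP cytometry entry are partly redacted.

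**Conclusion.** The point holds for rituximab. E 21 as written can admit a patient with unrecovered CD19-positive B cells more than 24 weeks after the last dose, and 8.8.1 prohibits that patient.

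The severity is minor. The documents give no rate of prior rituximab use, so the number affected is unknown. My judgement that it is very small rests on three things having to coincide: earlier rituximab beyond 24 weeks, persistent B-cell depletion, and a site that does not apply 8.8.1. The sample size, power, alpha and treatment comparisons do not depend on this.

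For prednisone there is no conflict, only room for a clearer pointer.

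**What to change.** Extend the rituximab parenthesis in E 21 with: *or last rituximab dose more than 24 weeks before screening without recovery of CD19-positive B lymphocytes*. This adds no new requirement, since 8.8.1 already sets the condition, and the downside is negligible.

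Optionally, let E 20 cross-refer to 8.8.2 for corticosteroids. A cross-reference is better than copying the parenthesis from 8.8.1, because 8.8.2 also carries the requirement of a stable dose for at least 4 weeks before randomization. An exemption in E 20 stating the dose alone would pass a patient on 10 mg/day or less whose dose had recently changed, whom 8.8.2 does not permit.

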8 STUDY TREATMENTS

8.1 INVESTIGATIONAL MEDICINAL PRODUCT(S)

A complete description of the Investigational Medicinal Product (IMP) and its proper handling will be provided in a pharmacy manual.

- Pharmaceutical form
 - SAR156597 solution for injection at 100 mg/mL: SAR156597 is supplied as a sterile freeze-dried powder for solution for injection. Each vial is overfilled with 125 mg of SAR156597 freeze-dried powder, and the final solution for injection is obtained by reconstitution of the entire vial content with 1.1 mL of water for injection, leading to an amount of 125 mg of SAR156597 drug substance in a total volume of 1.25 mL, that is a 100 mg/mL of SAR156597 solution. 1 mL of this 100 mg/mL SAR156597 solution can then be withdrawn for dose administration. 2 drug product vials are thus needed to reach a 200 mg dose.
 - Placebo consists of liquid with the same excipients as those of the reconstituted SAR156597 formulation, filled at nominal volume of 1.5 mL. Two vials are necessary, 1 mL will be taken from each vial to prepare 2 mL syringe.
- Method of preparation

At the study site, reconstitution of the IMP must be done by personnel other than those administering the drug and making clinical observations (e.g. pharmacist) to maintain the treatment blind (Refer to [Section 8.4](#)).

- At patient's home, reconstitution must be done by healthcare professionals (e.g. visiting nurse) out of view of patients and their families/caregivers.
- The IMP should be reconstituted the day of dosing (no more than 3 hours prior to SC injection), at room temperature.
- Dose of drug per administration
 - SAR156597 qw arm: one injection of SAR156597 200 mg administered subcutaneously every week
 - SAR156597 q2w arm: one injection of SAR156597 200mg administered subcutaneously once every 2 weeks alternating with one injection of placebo administered subcutaneously once every 2 weeks
 - Placebo arm: one injection of placebo administered every week

- Route and method of administration

The route and method of administration are subcutaneous in the abdomen. Subcutaneous injection sites should be alternated between the 4 quadrants of the abdomen (avoiding navel and waist areas) so that the same site is not injected for two consecutive weeks. Exact site of each injection will be documented on source document.

The IMP is administered every 7 days +/- 2 days from initial IMP administration. This is permitted per protocol to accommodate special circumstances, eg. laboratory results pending, ongoing AE, patient scheduling difficulty.

If IMP administration is missed or temporarily discontinued, the initial schedule of injections should be resumed. This does not apply to permanent treatment discontinuation.

On days when the patient has a study visit, the IMP will be administered by the Investigator or delegate after clinic procedures and blood collection.

For doses not administered at the study site, the IMP will be administered by qualified site personnel and /or healthcare professionals (e.g. visiting nurse service).

Patients should be monitored by site personnel/visiting nurse for at least 30 minutes after each administration for potential signs and symptoms that may suggest a hypersensitivity reaction.

[For Czech Republic only per local requirement: Patients should be monitored at the study site by site personnel for a minimum of 2 hours after the first administration of IMP and for a minimum of 1 hour after the next 5 administrations for potential signs and symptoms that may suggest a hypersensitivity reaction. For the subsequent IMP administrations, patients should be monitored by site personnel/visiting nurse for at least 30 minutes after each administration.]

For doses not given at study site, a booklet will be provided to the patient to record information related to the injections; this booklet will be completed by the visiting nurse after each injection and will be kept as source data in the patient's study file. Patients will be instructed to bring the booklet back at the subsequent site visit for Investigator's review.

